## 1. PROTOCOL ABSTRACT

Name of company:			
Boehringer Ingelheim			
Name of product:		1	
Stiolto/Spiolto			Boehringer Ingelheim
Name of active ingre	dient:	†	
Tiotropium bromide +	Olodaterol		
Protocol date:	Study number:	Version/Revision:	Version/Revision date:
19 February 2020	1237-0093	1.0	NA
	heim International GmbH	confidential information  I or one or more of its affiliated comp , reproduced, published or otherwise used with	
Effectiveness and Safety of Maintenance Treatment with Combination of Tiotropium and Olodaterol in Comparison to Maintenance Treatment with Combination of Inhaled Corticosteroids and Long-acting β2 agonists in COPD patients			ance Treatment with a
Team member Epidemiology:			
Project team:	, (I	Principal Investigator)	

literature.

c31403012-01

Proprietary confidential information © 2020 Boehringer Ingelheim International GmbH or one or more of its affiliated companies

Name of company:			
Boehringer Ingelhein	n		
Name of product: Stiolto/Spiolto			Boehringer Ingelheim
Name of active ingr Tiotropium bromide			
Protocol date:	Study number:	Version/Revision:	Version/Revision date:
19 February 2020	1237-0093	1.0	NA
© 2020 Boehringer Ing This document may not	elheim International GmbH - in full or in part - be passed on,	confidential information or one or more of its affiliated comp reproduced, published or otherwise used we increasingly involves multiple to	ithout prior written permission

19 February 2020	1237-0093	1.0	NA
© 2020 Boehringer Ingell This document may not - in	heim International GmbH n full or in part - be passed on,	confidential information or one or more of its affiliated comp reproduced, published or otherwise used with	thout prior written permission
The primary objective is to compare the effectiveness of maintenance therapy initiation with the combination treatment Tiotropium and Olodaterol (Olo+Tio) compared with LABA/ICS combination in COPD as the time to the first COPD exacerbation.  Secondary objectives are to compare patients treated with Tio+Olo and patients treated with LABA/ ICS combination: (1) Time to community acquired pneumonia, (2) time to escalation to triple therapy (3) time to an adverse outcome including exacerbation, escalation to triple therapy, or pneumonia, and (4) healthcare utilization outcomes and an analysis of all-cause and COPD-specific cost overall and by care setting.  Additionally, the study will investigate the effect modification of circulating eosinophil levels and exacerbation history on the safety and effectiveness of Tio+Olo compared with any LABA/ICS. Analyses will be repeated in subgroups of patients under high or low risk of exacerbation based on previous history of exacerbations in the year preceding cohort entry (with exacerbation history defined as either 1+ hospitalization or 2+ exacerbations in emergency department or outpatients settings [R05-1384]), as well as based on circulating eosinophils (cut-off: B-Eos 300cells/uL [P18-09975]) overall and among those without a history of exacerbation.			
Study design:	A incident new-user cohort design will be used, with confounding controlled via fine stratification and reweighting of time-conditional propensity scores		

Proprietary confidential information © 2020 Boehringer Ingelheim International GmbH or one or more of its affiliated companies

Name of company:			
Boehringer Ingelheim			
Name of product: Stiolto/Spiolto			Boehringer Ingelheim
Name of active ingre Tiotropium bromide +			
Protocol date:	Study number:	Version/Revision:	Version/Revision date:
19 February 2020	1237-0093	1.0	NA
© 2020 Boehringer Ingell This document may not - in	heim International GmbH n full or in part - be passed on,	confidential information or one or more of its affiliated compreproduced, published or otherwise used w	ithout prior written permission
The cohort will include all patients with a diagnosis of COPD who received at least one dispensing of a long-acting bronchodilator, Tio+Olo, LABA or for an inhaled corticosteroid from 1 January 2013 until 31 March 2019 (or the most recent date available at the time of cohort extraction). Only fixed-dose combinations products will be included in the main analyses. To increase the likelihood of a diagnosis of COPD, we only include patients 40 years of age or older at initiation of study treatment (i.e., the index date) and exclude all patients with a diagnosis of asthma within the baseline year or lung cancer, interstitial lung disease, or lung transplantation at any time prior to the index date.  Patients will need to have at least one year of medical and pharmacy health plan eligibility prior to the date of Tio+Olo or LABA/ICS initiation (index date) to allow the identification of new use and the measurement of baseline covariates. Patients will be followed until switching to the other treatment, the end of the individual's health plan eligibility, escalation of therapy, discontinuation of COPD treatment, or the end of the study period, whicheve occurs first. Main analyses will be limited to the first year following the index date.  Additional restriction to individuals who have laboratory test result data showing eosinophil levels will occur for relevant sensitivity analyses.			
Study data source:	The HealthCore Integ	grated Research Database SM (H	IRD)
Expected study size:	Overall: New users of Tio+Ol New users of LABA/l With eosinophil resul New users of Tio+Ol New users of LABA/l	ICS: 53,432 It data: o: 2,207	

Proprietary confidential information © 2020 Boehringer Ingelheim International GmbH or one or more of its affiliated companies

Name of company:					
Boehringer Ingelheim					
Name of product:					
Stiolto/Spiolto			Boehringer Ingelheim		
Name of active ingre	dient:				
Tiotropium bromide +					
Protocol date:	Study number:	Version/Revision:	Version/Revision date:		
19 February 2020	1237-0093	1.0	NA		
	Proprietary confidential information © 2020 Boehringer Ingelheim International GmbH or one or more of its affiliated companies. All rights reserved.  This document may not - in full or in part - be passed on, reproduced, published or otherwise used without prior written permission				
Main criteria for inclusion:	Trannary 7013 and March 7019				
inclusion:	- Diagnosis of COPD	and age $\geq$ 40 years			
	-Less than one year of medical history information prior to the index date -Asthma diagnosis within one year prior to the index date				
Main criteria for exclusion:	-Lung cancer, interstitial lung disease, or lung transplantation at any time prior to the index date				
	-Use of triple therapy (LABA/LAMA/ICS) prior to the index date				
Comparison groups:	Initiating Tio+Olo compared to initiating LABA/ICS therapy				
Expected duration of exposure:	Analyses will be limited to one year following the index date for the primary and secondary analyses. Sensitivity analyses will use all available exposure data.				

#### 2. LIST OF ABBREVIATIONS AND TERMS

BI Boehringer Ingelheim
BMI Body Mass Index
CI Confidence Interval

COPD Chronic Obstructive Pulmonary Disease
CPRD Clinical Practice Research Datalink

DSAs Data Sharing Agreements
ED Emergency Department
FDC Fixed Dose Combination

FTCO First Treatment Carry-On Analysis

HIPAA Health Insurance Portability and Accountability Act

HIRD HealthCore Integrated Research Database

HR Hazard Ratio

ICD-9 International Classification of Disease, Version 9
ICD-10 International Classification of Disease, Version 10

ICS Inhaled Corticosteroids

IR Incidence Rate

IRB Institutional Review Board

ITT Intention to Treat

LABA Long-acting Beta2-agonist

LAMA Long-acting Muscarinic Antagonists

N Number

NDI National Death Index

PHI Protected Health Information

PS Propensity Score

RR Rate Ratio

SOPs Standard Operating Procedures

cells/µL Microliter
US United States

Proprietary confidential information © 2020 Boehringer Ingelheim International GmbH or one or more of its affiliated companies

#### 4. AMENDMENTS AND UPDATES

There are currently no amendments to the protocol.

#### 5. MILESTONES

Milestone	Planned date
Start of data collection: Data extraction and coding	August 1, 2019
End of data collection:	March 31, 2019*
Study progress report(s) as referred in Article 107m(5) of Directive 2001/83/EC:	Not applicable
Interim report(s) of study results:	Not applicable
Registration in the EU PAS register	Not applicable
Final report of study results:	April 2020 (Preliminary results: 19 December 2019)

\* This is an observational study based on existing data collected in the form of administrative claims. The date listed reflects the expected end of data availability at the start of analysis.

#### 6. RATIONALE AND BACKGROUND

Chronic obstructive pulmonary disease (COPD) is a leading cause of morbidity and mortality throughout the world [P07-11503]. It has recently risen to become the third leading cause of death in the US [R13-1383]. Long-acting bronchodilator medications, that include long-acting beta2-agonists (LABAs) and the long-acting muscarinic antagonists (LAMAs) such as the anticholinergic tiotropium, have become central maintenance therapy to the management of COPD, with inhaled corticosteroids (ICS) added with increasing severity [P07-11503].

The treatment of COPD increasingly involves multiple therapies including long-acting bronchodilators (LAMAs and LABAs) and inhaled corticosteroids (ICS) with combinations of these drugs now formulated into single inhalers. Optimal treatment choice appears to be influenced by a variety of factors including exacerbation risk. Although the use of ICS has increased disproportionately with respect to COPD treatment guidelines, it may be appropriate only in a subset of these users [P15-12888; P16-12287]. For example, the recent FLAME randomized trial reported that patients receiving the LABA/LAMA combination had fewer exacerbations than those receiving the LABA/ICS combination over a one-year follow-

Proprietary confidential information © 2020 Boehringer Ingelheim International GmbH or one or more of its affiliated companies

up period. In the WISDOM trial, in patients on triple therapy the risk of moderate or severe exacerbations was similar among those who discontinued and those who continued ICS. The ENERGITO study showed significant improvements in lung function with the LAMA/LABA FDC Tio+Olo versus LABA/ICS. Further, pneumonia associated with long-term ICS use increases the risk of hospitalization, and is associated with substantial increases in cost [P07-09514; R18-2874].

Although, a recent population-based observational study showed no difference in exacerbation risk for COPD patients with B-Eosinophils below 300 cells/uL) if treated either with LAMA or LABA/ICS [P18-09975], this data have yet to be confirmed in population based studies in real world conditions. Given high-cost adverse events associated with long-term use of ICS and inconsistent evidence concerning whether there is a clinically relevant benefit of ICS combination therapy in terms of disease control, it is important to assess differences between subsets of COPD patients in terms of the effectiveness and cost of LABA/ICS combination therapies versus other non-ICS options, such as Tiotropium+Olodaterol (Tio+Olo).

The proposed study will investigate the comparative effectiveness of Tio+Olo vs any LABA /ICS combination in COPD, describe differences in healthcare utilization, and compare cost effectiveness. Whether associations with time to exacerbation, community acquired pneumonia, escalation to triple therapy, and adverse outcome are modified by exacerbation risk (measured based on individual history and eosinophil levels) will also be assessed.

## 7. RESEARCH QUESTIONS AND OBJECTIVES

The goal of this study is to investigate the risk of COPD exacerbations, community acquired pneumonia, and health care utilization in patients treated with Tio+Olo in comparison to patients treated with LABA/ICS combination therapy. All analyses will be conducted for the total population, as well as in sub-groups of patients under high- or low risk of exacerbation based on (1) previous history of exacerbations in the year preceding cohort entry (cut-off: 0-1 vs 2+ exacerbations [R05-1384], (2) circulating eosinophils (cut-off B-Eos 300 cells/uL [P18-09975]), and (3) as an exploratory analysis, a combination of exacerbation history and circulating eosinophils.

#### Primary objective:

The primary objective is to compare the effectiveness of new use of maintenance therapy initiation with the combination treatment Tiotropium and Olodaterol (Tio+Olo) compared with new use of LABA/ICS combination in COPD as the time to the first COPD exacerbation.

#### Secondary objectives:

Secondary objectives are to compare patients treated with Tio+Olo and patients treated with LABA/ICS combination therapy with respect to:

Time to first community acquired pneumonia,

Time to escalation to triple therapy, and

**BI Study Number 1237-0093** 

c31403012-01

Proprietary confidential information © 2020 Boehringer Ingelheim International GmbH or one or more of its affiliated companies

Time to an adverse outcome including exacerbation, pneumonia, or escalation to triple therapy

#### Exploratory objective:

To assess differences between Tio+Olo vs any LABA/ICS combination in all-cause and COPD-specific healthcare utilization and cost overall and by care setting

#### 8. RESEARCH METHODS

#### 8.1 STUDY DESIGN

Population-based propensity score-matched new-user cohort study.

#### 8.2 SETTING

The study will be conducted using administrative healthcare claims and laboratory result data captured in the HealthCore Integrated Research Database (HIRD; details in Section 8.5). The observation period will be from January 2013 until the most recent date available at the time that the cohort is extracted (estimated March 2019).

#### **8.3 PATIENTS**

The study cohort will be formed based on the following entry criteria.

#### *Inclusion Criteria:*

- 1. At least one prescription for Tio+Olo combined inhaler or a LABA/ICS combined inhaler between 1 January 2013 and 31 March 2019.
  - a) The first dispensing of either Tio+Olo or LABA/ICS combined inhaler will be defined as the index date.
  - b) For the main analyses, only fixed dose combination (FDC) inhalers will be included. Sensitivity analyses will also accept free combinations of LABA/ICS.
- 2. At least one diagnosis of COPD at any time prior to the index date.
- 3. At least one year of continuous medical and pharmacy health plan eligibility prior to the index date will be required to allow a baseline period for the covariates and identification of new use of the study drugs.

#### Exclusion Criteria:

- 1. To increase the likelihood of a true diagnosis of COPD, we will exclude:
  - a) All patients less than 40 years of age on the index date, and
  - b) All patients with a diagnosis of asthma in the year prior to the index date
- 2. To limit the population to those without severe lung compromise outside of COPD, we will exclude individuals with lung cancer, interstitial lung disease, or lung transplant identified at any time prior to the index date
- 3. To restrict the cohort to new users of Tio+Olo or LABA/ICS, we will exclude any individual with use of either Tio+Olo, LABA/ICS, or LABA/LAMA/ICS

combination therapy in free or fixed form for at least one year prior to the index date.

Outpatient laboratory data is available for a subset of patients. Some analyses will be further restricted to the subset of the population with at least one laboratory result showing circulating eosinophil levels within six months before the index date.

Individuals in the study cohort will be followed from the index date until the earliest of the date of a switch in treatment, addition of either an ICS for the Tio+Olo group or of LAMA to the LABA/ICS group, discontinuation of COPD treatment, the end of the study period, or the end of continuous health plan eligibility. Main analyses will be further limited to the first year after cohort entry, with sensitivity analyses considering all available data.

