#### 8.5 DATA SOURCES

This study will be conducted using the HIRD, a large administrative healthcare database maintained by HealthCore for use in health outcomes and pharmacoepidemiologic research. The HIRD includes longitudinal medical and pharmacy claims data from health plan

members across the United States (US). Member enrollment, medical care (professional and facility claims), outpatient prescription drug use, outpatient laboratory test result data, and health care utilization may be tracked for health plan members in the database dating back to January 2006, and with diagnoses recorded in International Classification of Disease, Version 10 (ICD-10) since October, 2015. Laboratory result data are additionally available for those tests that have been performed using two large, national reference laboratories (Quest and LabCorp) [R14-4278]. The database has been used for the study of numerous diseases, including studies of COPD [R19-2324; R19-2321; R19-2323; R19-2322; P15-11025; P14-12233].

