#### 8.7 STUDY SIZE

Preliminary counts of FDC Tio+Olo and ICS/LABA users in the HIRD are shown here:

	Tio+Olo		ICS/LABA	
	N	%	N	%
New users	8,233	100.0	341,352	100.0
At least 12 months of pre-index eligibility	6,263	76.1	187,093	54.8
Age 40+	6,126	97.8	136,310	72.9
At least 1 diagnosis of COPD	5,469	89.3	53,432	39.2
At least 1 eosinophil % result prior to the index date	2,207	40.4	19,407	36.3
Eosinophil result (N, % of those with				
a result)				
0-2%	1,059	48.0	8,907	45.9
2-4%	745	33.8	6,698	34.5

D 1	' C	Y 11 1 Y 1	0 177	01. 011. 1
Proprietary confidential	information © 2020 Boehring	ger Ingelheim International	GmbH or one or more of	of its affiliated companies

4%+	403	18.3	3,802	19.6
Eosinophil result, patients with low				
exacerbation history(0 inpatient and				
0-1 outpatient events at baseline, N,				
%)				
<300 cells/uL	1,381	30.0	12,351	27.1
≥300 cells/uL	481	10.5	4,437	9.7
Unknown	2,739	59.5	28,733	63.1
Eosinophil result, patients with high				
exacerbation history (1+ inpatient or				
2+ outpatient events at baseline, N,				
%)				
<300 cells/uL	226	26.0	1,820	23.0
≥300 cells/uL	105	12.1	670	8.5
Unknown	537	61.9	5,421	68.5

In a recent analysis of the risk of exacerbations based on Clinical Practice Research Datalink (CPRD), a total of 2,000 patients per cohort detected a 15% difference in risk of a first exacerbation (hazard ratio 0.85) with over 90% power. As such, overall analyses are expected to have adequate power. Analyses that are stratified based on the presence of claims-based indicators of exacerbation and/or limited to individuals with specific eosinophils levels will be more limited. Given low expected sample size, stratification by eosinophil results within individuals with exacerbations at baseline will not be performed.

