### **ANNEX 3.3: DEFINITIONS OF STUDY COVARIATES**

See section 8.4.3. Complete list of codes will be added to this document after review and approval.

Medication	HCPCS	GPI
Short-acting beta- agonists		
Levalbuterol	J7617J7607J7612, J7614,J7615	4420104510X 4420104550X
Albuterol	J7602, J7603, J7609-J7611, J7613, J7616, J7620, J7625, Q4093, Q4094	4420101000X 4420101010X
Terbutaline	J3105J7680,J7681	442010602X
Isoproterenol	J7657 J7658 J7659	44201040X

	J7660	
Methylxanthines		
A minanhyllina		4430001000x
Aminophylline		4430001010x
		4430004000x 499100240X 4499100220X
		4499100242X 4499100250X 44992203X
Theophylline (SR)	J2810	44993003X 44993204X 44999003X
		44999602X 4499220310X 4499960270X
		4499220315X
SAMA (Short-acting muscarinic antagonists)		
Ipratropium bromide	J7644, J7655	4230X 44100030X
Antibiotics for a respiratory condition		
Aamikacin	J0278	07000010x
Amoxicillin/potassium clavulanate		0199000220x
Amoxicillin		01200010x
Ampicillin	J0290	01200020x
Ampicillin-sulbactam	J0295	0199000225x
Azithromycin	J0456	03400010x
Aztreonam	S0073	16000005x
Cefaclor		02200040x
Cefdinir		02300040x
Cefepime	J0692	02400040x
Cefixime		02300060x
Cefotaxime	J0698	02300075x
Cefpodoxime		02300065x
Cefprozil		02200062x
Ceftazidime	J0713, J0714	02300080x
Ceftriaxone	J0696	02300090x

c31403012-01

Cefuroxime	J0697	02200065x
Ciprofloxacin	J0744	05000020x
Clarithromycin		03500010x
Doxycycline		04000020x
Ertapenem	J1335	16150030x
Erythromycin	J1364	0310x
Gemifloxacin		05000083x
Imipenem	J0743	16159902x
Levofloxacin	J1956	05000034x
Linezolid	J2020	16230040x
Meropenem	J2185	16150050x
Moxifloxacin	J2280	05000037x
Penicillin G benzathine	J0561, J0558	01990002x, 01100020x
Penicillin VK		01100040x
Piperacillin	S0081	01400040x
Piperacillin-tazobactam	J2543	019900027x
Procaine penicillin	J0558, J2510	
Ticarcillin		01400050x
Ticarcillin-clavulanate	S0040	019900023x
Trimethoprim- sulfamethoxazole	S0039	169900023x
Vancomycin	J3370	16000060102x

Condition	ICD9	ICD10	ICD9 proc	ICD10 proc	HCPC S	CPT
Asthma	493	J45				
	493	J45.2				
	493	J45.20				
	493.01	J45.21				
	493.02	J45.22				
	493.1	J45.3				
	493.1	J45.30				

		<del> </del>	1	1	1	1
	493.11	J45.31				
	493.12	J45.32				
	493.2	J45.4				
	493.2	J45.40				
	493.21	J45.41				
	493.22	J45.42				
	493.8	J45.5				
	493.81	J45.50				
	493.82	J45.51				
	493.9	J45.52				
	493.9	J45.9				
	493.91	J45.90				
	493.92	J45.901				
		J45.902				
		J45.909				
		J45.99				
		J45.990				
		J45.991				
		J45.998				
Lung cancer	162	C33				

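### The code rows printed in Annex 3.3 do not implement Exclusion 2: the interstitial lung disease row omits the common adult forms, and the ICD-10 lung cancer row omits right- and left-sided codes

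*Combined protocol and SAP*

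**What the plan says.** Section 8.3, Exclusion Criteria item 2, states that "we will exclude individuals with lung cancer, interstitial lung disease, or lung transplant identified at any time prior to the index date". Its purpose is given as "To limit the population to those without severe lung compromise outside of COPD". Nothing limits it by subtype, side or age at diagnosis. Item 1 of the same list also removes "All patients less than 40 years of age on the index date", so the criterion operates in middle-aged and older adults.

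The codes are in Annex 3.3, which opens with the note "Complete list of codes will be added to this document after review and approval". The rows for this criterion are nevertheless filled in:

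- **ILD:** ICD-9 516.6* and 516.34; ICD-10 J84.115, J84.83, J84.841, J84.842, J84.843 and J84.848.
- **Lung cancer:** ICD-9 162, 231.2, 197.0, 176.4, 235.7 and V10.11; ICD-10 C33, C34.00, C34.10, C34.2, C34.30, C34.80, C34.90, C46.50, C78.00, D02.20, D38.1 and Z85.118.

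Section 8.5 describes data back to January 2006, "with diagnoses recorded in International Classification of Disease, Version 10 (ICD-10) since October, 2015". Index dispensings fall "between 1 January 2013 and 31 March 2019". The feasibility table in Section 8.7 ends its eligibility steps at "At least 1 diagnosis of COPD 5,469 89.3 53,432 39.2" and has no step for Exclusion 2.

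**The concern.** The written criterion is broad and the printed codes are narrow. A programmer who applied the rows as they stand would leave in the cohort many of the adults whom Section 8.3 declares ineligible, and nothing in the attrition table would reveal it.

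The main consequence is for the primary outcome. In Section 8.4.2.1 a hospitalization needs a principal COPD discharge diagnosis and an emergency visit needs a COPD discharge diagnosis. The third route, an antibiotic and an oral corticosteroid dispensed on one day, needs no COPD diagnosis. Such dispensings to a patient with ILD would be counted as COPD exacerbations. The same section argues that loss of outcome specificity is the more serious threat and biases toward the null. ILD is not among the covariates named in Section 8.4.4, so the prespecified part of the propensity score does not account for it.

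**Working it through.** **Basis.** The annex prints codes without labels. The meanings below are the standard ICD labels, taken as an assumption that a coder can confirm in minutes.

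**The plan's own figures.** No count is given for Exclusion 2. The last eligibility step in Section 8.7 reproduces: 5,469 / 6,126 = 89.3% and 53,432 / 136,310 = 39.2%. These counts have no step for ILD or lung cancer, so they say nothing about how the rows perform.

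**ILD row.**

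| Meaning | ICD-9 entries | ICD-10 codes |
|---|---|---|
| Childhood ILD | 516.6* | J84.841, J84.842, J84.843, J84.848 |
| Surfactant mutations | – | J84.83 |
| Respiratory bronchiolitis ILD | 516.34 | J84.115 |

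Only 1 of 2 ICD-9 entries and 1 of 6 ICD-10 codes describe a mainly adult form. Pulmonary fibrosis (515, J84.10), idiopathic pulmonary fibrosis (516.31, J84.112), the other J84.11x forms and unspecified ILD (J84.9) are not listed.

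**Lung cancer row, ICD-10.** Of 12 codes, 8 are unspecified-side versions: C34.00, C34.10, C34.30, C34.80, C34.90, C46.50, C78.00 and D02.20. The other 4 (C33, C34.2, D38.1 and Z85.118) carry no side. No right or left code is present.

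**Is this shorthand for a family?** The annex suggests not. It uses wildcards where a family is meant (516.6*, E78.%%, C00%-C76% in the Cancer row). It lists sides one by one where sides are meant (C44.211, C44.212, C44.219). On that convention C34.10 matches only C34.10, and a right-sided C34.11 would count toward the Cancer covariate without triggering the exclusion. No matching rule is stated.

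**Calendar reach of the lung cancer gap.** The intake window is 6 × 12 + 3 = 75 months. ICD-10 covers October 2015 to March 2019, 3 + 36 + 3 = 42 months, and 42 / 75 = 56%. ICD-9 records from January 2006 to September 2015 (9 × 12 + 9 = 117 months) remain usable in the look-back.

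**How much lung cancer leaks.** One listed code at any prior time excludes. If a patient has k claims with C34 codes that have sided versions, and each independently has probability u of being unspecified-side, the chance of exclusion is 1 − (1 − u)^k. Both u and k are assumptions.

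| u | k = 5 | k = 20 | k = 40 |
|---|---|---|---|
| 2% | 10% | 33% | 55% |
| 5% | 23% | 64% | 87% |
| 20% | 67% | 99% | about 100% |

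The range runs from poor capture to near-complete capture. The documents cannot narrow it.

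**The case against.** **The list is declared incomplete.** This stands in part: the rows are not proof of what the final list will do. But they are filled in, Annex 1 names no stand-alone code document, and Section 5 plans extraction and coding from 1 August 2019 and preliminary results on 19 December 2019. Both dates precede this version of 19 February 2020. A note that more codes will follow does not correct rows already printed.

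**The text may be damaged.** The ILD row breaks across pages, and repeated entries such as 493 suggest lost trailing zeros. But its ICD-9 and ICD-10 columns cover the same conditions, which makes lost adult codes unlikely. For lung cancer, "Lung cancer 162 C33" leaves open whether 162 means the whole category. In the same row 197.0 keeps its zero, which favours the category reading.

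**Other parts of the plan compensate.** For lung cancer this is partly right. The Cancer covariate covers every C34 code. Calendar year is a covariate and the score is time-conditional, which softens the concern that the criterion shifts at the ICD-10 change. High-dimensional selection might also pick up an ILD code, but that is not assured, and adjustment does not restore outcome specificity.

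**A stronger reading is tempting.** A reader might infer that the row finds only unspecified-side lung cancer and that most lung cancer patients would stay. The documents do not support this: ICD-9 162, C33, C34.2, D38.1 and Z85.118 are listed, and a single qualifying claim is enough. A reader might also put a number on retained patients, but no prevalence is given for either disease.

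**Conclusion.** The point holds, with different strength for the two diseases.

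- **ILD:** applied as printed, the row would miss most adult ILD in a cohort aged 40 or older. This rests on the standard ICD labels and on the row being intact.
- **Lung cancer:** patients whose ICD-10 records carry only right- or left-sided codes, with no other listed code, would be retained. The gap is real if bare codes match exactly, but its size is unknown and adjustment partly offsets it.

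No count of retained patients and no shift in the hazard ratio can be derived from the documents. The route to bias is specific: false moderate exacerbations through the same-day dispensing rule, mainly in retained ILD patients. This is a correctable defect in the current code list, not a fault in the criterion itself.

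**What to change.** When completing Annex 3.3:

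1. Replace the ILD row with an adult-inclusive list, for example ICD-9 515 and 516.x and ICD-10 J84.%. The exact membership is a coding decision to record.
2. For lung cancer, write ICD-9 162.x and ICD-10 C34.%, C78.0%, D02.2% and C46.5% in place of the bare or unspecified-side entries, and keep the remaining codes.
3. State whether a code without a wildcard matches exactly or as a family.
4. Reapply Exclusion 2 and add its row, by treatment group, to the Section 8.7 attrition table.

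The cost is a code-list edit and a rerun of cohort selection, weighting and analyses. The expected loss is small and confined to patients whom Section 8.3 already makes ineligible. If the cohort has already been extracted, the new attrition row will show how many were affected.
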